10.1.8. Data Quality Assurance

- All participant data relating to the study will be recorded on printed or eCRF unless transmitted to the sponsor or designee electronically (e.g., laboratory data). The investigator is responsible for verifying that data entries are accurate and correct by physically or electronically signing the eCRF.
- Guidance on completion of eCRFs will be provided in eCRF Completion Guidelines.

- The investigator must permit study-related monitoring, audits, IRB/IEC review, and regulatory agency inspections and provide direct access to source data documents.
- Quality tolerance limits (QTLs) will be pre-defined in the Integrated Quality Risk Management Plan (IQRMP) to identify systematic issues that can impact participant safety and/or reliability of study results. These pre-defined parameters will be monitored during and at the end of the study and all deviations from the QTLs and remedial actions taken will be summarized in the clinical study report.
- Monitoring details describing strategy including definition of study critical data
 items and processes (e.g., risk-based initiatives in operations and quality such as Risk
 Management and Mitigation Strategies and Analytical Risk-Based Monitoring),
 methods, responsibilities and requirements, including handling of noncompliance
 issues and monitoring techniques (central, remote, or on-site monitoring) are
 provided in the Clinical Monitoring Plan.
- The sponsor or designee is responsible for the data management of this study including quality checking of the data. Detailed information about study data collection and management process including systems used can be found in the Data Management Plan.
- The sponsor assumes accountability for actions delegated to other individuals (e.g., Contract Research Organizations).
- Records and documents, including signed ICF, pertaining to the conduct of this study must be retained by the investigator for 25 years from the issue of the final Clinical Study Report (CSR)/equivalent summary unless local regulations or institutional policies require a different retention period. No records may be destroyed during the retention period without the written approval of the sponsor. No records may be transferred to another location or party without written notification to the sponsor.
- When copies of source documents are shared externally for review by a central reader mechanism (e.g., endpoint adjudication committee; expert reader), documents are stored by the external body for 25 years.

10.1.9. Source Documents

- Source documents provide evidence for the existence of the participant and substantiate the integrity of the data collected. Source documents are filed at the investigator's site.
- Data reported on the eCRF or entered in the eCRF that are transcribed from source documents must be consistent with the source documents or the discrepancies must be explained. The investigator may need to request previous medical records or transfer records, depending on the study. Also, current medical records must be available.
- Definition of what constitutes source data, and its origin can be found in the sitespecific Source Data Acknowledgment.
- The investigator must maintain accurate documentation (source data) that supports the information entered in the eCRF.

Study monitors will perform ongoing source data verification to confirm that data
entered into the eCRF by authorized site personnel are accurate, complete, and
verifiable from source documents; that the safety and rights of participants are being
protected; and that the study is being conducted in accordance with the currently
approved protocol and any other study agreements, ICH GCP, and all applicable
regulatory requirements.

10.1.10. Study and site start and closure

First Act of Recruitment

The start of study is defined as first subject first visit (FSFV) at a country-level.

Study/Site Termination

GSK or designee reserves the right to close the study site or terminate the study at any time for any reason at the sole discretion of GSK. Study sites will be closed upon study completion. A study site is considered closed when all required documents and study supplies have been collected and a study-site closure visit has been performed.

The investigator may initiate study-site closure at any time, provided there is reasonable cause and sufficient notice is given in advance of the intended termination.

Reasons for the early closure of a study site by the sponsor or investigator may include but are not limited to:

For study termination:

• Discontinuation of further study intervention development

For site termination:

- Failure of the investigator to comply with the protocol, the requirements of the IRB/IEC or local health authorities, the sponsor's procedures, or GCP guidelines
- Inadequate or no recruitment (evaluated after a reasonable amount of time) of participants by the investigator
- Total number of participants included earlier than expected

If the study is prematurely terminated or temporarily suspended, the sponsor shall promptly inform the investigators, the IECs/IRBs, the regulatory authorities, and any contract research organization(s) used in the study of the reason for termination or temporary suspension, as specified by the applicable regulatory requirements. The investigator shall promptly inform the participant and should assure appropriate participant therapy and/or follow-up.

10.1.11. Publication Policy

• GSK seeks to publish medically or scientifically significant results in searchable peer-reviewed scientific literature within 18 months from LSLV. We follow

International Committee of Medical Journal Editors standards for authorship and use Good Publications practices to guide our publications.

- The sponsor will comply with the requirements for publication of study results. In accordance with standard editorial and ethical practice, the sponsor will generally support publication of multicenter studies only in their entirety and not as individual site data. In this case, a coordinating investigator will be designated by mutual agreement.
- Authorship will be determined by mutual agreement and in line with International Committee of Medical Journal Editors authorship requirements.

10.2. Appendix 2: Clinical Laboratory Tests

- The tests detailed in Appendix Table 1 will be performed by the central laboratory Q2 Solutions.
- Local laboratory results are only required in the event that the central laboratory results are not available in time for either study intervention administration and/or response evaluation. If a local sample is required, it is important that the sample for central analysis is obtained at the same time. Additionally, if the local laboratory results are used to make either a study intervention decision or response evaluation, the results must be recorded.
- Protocol-specific requirements for inclusion or exclusion of participants are detailed in Section 5 of the protocol.
- Additional tests may be performed at any time during the study as determined necessary by the investigator or required by local regulations.
- Investigators must document their review of each laboratory safety report.

Appendix Table 1 Protocol-Required Safety Laboratory Tests

Laboratory Assessments	Parameters				
Haematology ¹	Platelet Count	RBC Indices:		WBC count with Differential: (post-dose results blinded asdescribed in footnote 1)	
	RBC Count	MCV	WBC		
	Haemoglobin	MCH	Neutrophils		
	Haematocrit	%Reticulocytes	Lymphocytes		
			Monocytes		
			Eosinophils		
			Basophils		
Clinical Chemistry ²	BUN	Potassium	AST(SGOT)	Total and directbilirubin	
	Creatinine	Sodium	ALT (SGPT)	Total Protein	
	Glucose (non-fasting)	Calcium	Alkaline	Albumin	
			phosphatase ³		
		Magnesium	GGT		
Routine Urinalysis Pregnancy testing	Specific gravity pH, glucose, protein, blood, ketones by dipstick Microscopic examination and UACR (if blood or protein is abnormal[evidence of microalbuminuria or haematuria of ≥1+]) UACR will require a separate urine sample to be sent to central laboratory for analysis. Highly sensitive serum pregnancy test at Screening Visit 1, Exit Visit and at Early Withdrawal				
regnancy testing	Visit; highly sensitive urin	Visit; highly sensitive urine pregnancy tests for other assessments at time points specified in Table 1, and additionally within 24 hours prior to CT scan (as needed for WOCBP)			
Other Tests	FSH (if required to confirm postmenopausal status, see Section 10.4) Parasitic Screening (only required in regions with high-risk or for participants who have visited high-risk regions in the past 6 months). Sites should use local laboratories. If sites wish to use central laboratories, they should note that the central test is stool microscopy for ova and parasites. For details of the organisms detected by this test refer to the parasitic screening section of the SRM. Total IgE Complement (C3 and C4) Serum samples collected at baseline will be frozen and stored for later analyses, if necessary: anti-MPO antibody, anti-PR3 antibody, ANA including anti-dsDNA antibody				

Abbreviations: ALT, alanine aminotransferase; ANA, anti-nuclear antibody; AST, aspartate aminotransferase; BUN, blood urea nitrogen; FSH, follicle-stimulating hormone; MPO, myeloperoxidase; PR3, proteinase 3; SGOT, serum glutamic-oxaloacetic transaminase; SGPT, serum glutamic-pyruvic transaminase; UACR, urinary albumin-creatinine ratio; WBC, white blood cell; WOCBP, women of childbearing potential; WONCBP, women of non-childbearing potential; GGT, Gamma-glutamyl transferase.

- To maintain the treatment blind, the following data for post-randomization samples will not be reported to investigators and blinded Sponsor representatives: absolute and percentage values of eosinophils, neutrophils, lymphocytes, monocytes, and basophils.
- 2. Details of liver chemistry stopping criteria and required actions and follow-up assessments after liver stopping or monitoring event are given in Section 7.1.2 and Appendix 6. All events of ALT ≥3 × upper limit of normal (ULN) and total bilirubin ≥2 × ULN (>35% direct bilirubin) or ALT ≥3 × ULN and international normalized ratio(INR) >1.5, if INR measured, which may indicate severe liver injury (possible Hy's Law), must be reported to GSK as an SAE.
- 3. If alkaline phosphatase is elevated, consider fractionating.
- 4. Local urine testing will be standard for all visits (except Screening Visit and Exit Visit) unless serum testing is required by local regulation or IRB/IEC.

10.3. Appendix 3: AEs and SAEs: Definitions and Procedures for Recording, Evaluating, Follow-up, and Reporting

10.3.1. Definition of AE

AE Definition

- An AE is any untoward medical occurrence in a clinical study participant, temporally associated with the use of a study intervention, whether or not considered related to the study intervention.
- NOTE: An AE can therefore be any unfavourable and unintended sign (including an abnormal laboratory finding), symptom, or disease (new or exacerbated) temporally associated with the use of a study intervention.

Events Meeting the AE Definition

- Any abnormal laboratory test results (hematology, clinical chemistry, or urinalysis) or other safety assessments (e.g., ECG, radiological scans, vital signs measurements), including those that worsen from baseline, considered clinically significant in the medical and scientific judgment of the investigator (i.e., not related to progression of underlying disease).
- Exacerbation of a chronic or intermittent pre-existing condition including either an increase in frequency and/or intensity of the condition.
- New condition detected or diagnosed after study intervention administration even though it may have been present before the start of the study.
- Signs, symptoms, or the clinical sequelae of a suspected intervention-intervention interaction.
- Signs, symptoms, or the clinical sequelae of a suspected overdose of either study intervention or a concomitant medication. Overdose per se will not be reported as an AE/SAE unless it is an intentional overdose taken with possible suicidal/self-harming intent. Such overdoses should be reported regardless of sequelae.
- "Lack of efficacy" or "failure of expected pharmacological action" per se will not be reported as an AE or SAE. Such instances will be captured in the efficacy assessments. However, the signs, symptoms, and/or clinical sequelae resulting from lack of efficacy will be reported as AE or SAE if they fulfil the definition of an AE or SAE.

Events NOT Meeting the AE Definition

- Any clinically significant abnormal laboratory findings or other abnormal safety assessments that are associated with the underlying disease, unless judged by the investigator to be more severe than expected for the participant's condition.
- The disease/disorder being studied or expected progression, signs, or symptoms of the disease/disorder being studied, unless more severe than expected for the participant's condition.
- Medical or surgical procedure (e.g., endoscopy, appendectomy): the condition that leads to the procedure is the AE.
- Situations in which an untoward medical occurrence did not occur (social and/or convenience admission to a hospital).
- Anticipated day-to-day fluctuations of pre-existing disease(s) or condition(s) present or detected at the start of the study that do not worsen.

10.3.2. Definition of SAE

An SAE is defined as any untoward medical occurrence that, at any dose, meets one or more of the criteria listed:

a. Results in death

b. Is life-threatening

The term 'life-threatening' in the definition of 'serious' refers to an event in which the participant was at risk of death at the time of the event. It does not refer to an event, which hypothetically might have caused death, if it were more severe.

c. Requires inpatient hospitalization or prolongation of existing hospitalization

- In general, hospitalization signifies that the participant has been admitted (usually involving at least an overnight stay) at the hospital or emergency ward for observation and/or treatment that would not have been appropriate in the physician's office or outpatient setting. Complications that occur during hospitalization are AE. If a complication prolongs hospitalization or fulfills any other serious criteria, the event is serious. When in doubt as to whether "hospitalization" occurred or was necessary, the AE should be considered serious.
- Hospitalization for elective treatment of a pre-existing condition that did not worsen from baseline is not considered an AE.

d. Results in persistent or significant disability/incapacity

- The term disability means a substantial disruption of a person's ability to conduct normal life functions.
- This definition is not intended to include experiences of relatively minor medical significance such as uncomplicated headache, nausea, vomiting,

diarrhea, influenza, and accidental trauma (e.g., sprained ankle) that may interfere with or prevent everyday life functions but do not constitute a substantial disruption.

e. Is a congenital anomaly/birth defect

f. Is a suspected transmission of any infectious agent via an authorized medicinal product

g. Other situations:

- Possible Hy's Law case: ALT≥3x ULN AND total bilirubin ≥2x ULN (>35% direct bilirubin) or INR >1.5 must be reported as SAE
- Medical or scientific judgment should be exercised by the investigator in deciding whether SAE reporting is appropriate in other situations such as significant medical events that may jeopardize the participant or may require medical or surgical intervention to prevent one of the other outcomes listed in the above definition. These events should usually be considered serious.
 - Examples of such events include invasive or malignant cancers, intensive treatment for allergic bronchospasm, blood dyscrasias, convulsions, or development of intervention dependency or intervention abuse.

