7.1.2. Liver Chemistry Stopping Criteria

Liver chemistry stopping, and increased monitoring criteria have been designed to assure participant safety and evaluate liver event aetiology.

Discontinuation of study intervention for abnormal liver tests is required when:

[figure not shown]
- a participant meets one of the conditions outlined in Figure 2 and Figure 3
 OR
- in the presence of abnormal liver chemistry not meeting protocol specified stopping rules, if the investigator believes that it is in the best interest of the participant.

Study treatment restart or rechallenge after liver chemistry stopping criteria are met by any participant in this study is not allowed.

Details of liver chemistry stopping criteria, required actions, and follow-up assessments after liver stopping or monitoring event are given in Appendix 6.

218079

[figure not shown]
Figure 2 Liver Chemistry Stopping Criteria Algorithm

- Must refer to Liver Safety Required Actions and Follow up Assessments section in the Appendix
- Report within 24 hours
- ➤ If possible Hy's Law case: ALT≥3xULN and total bilirubin ≥2xULN (>35% direct) or INR>1.5* report as an SAE
 *INR value not applicable to participants on anticoagulants

Abbreviations: ALT, alanine transaminase; INR, international normalised ratio; Tbili, total bilirubin; SAE, serious adverse event; ULN, upper limit of normal

Figure 3 Liver Chemistry Increased Monitoring Algorithm with Continued Study Intervention for Participants with ALT ≥3x ULN but <8xULN and do not meet any of the liver stopping criteria

- Must refer to Liver Safety Required Actions and Follow up Assessments section in the Appendix
- Report within 24 hours
- ➤ If possible Hy's Law case: ALT≥3xULN and total bilirubin ≥2xULN (>35% direct) or INR>1.5* report as an SAE
 *INR value not applicable to participants on anticoagulants

Abbreviations: ALT, alanine transaminase; INR, international normalised ratio; Tbili, total bilirubin; SAE, serious adverse event; ULN, upper limit of normal

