8.4. Adverse Events (AEs), Serious Adverse Events (SAEs) and Other Safety Reporting

The definitions of an AE and SAE can be found in Appendix 3.

The definitions of device-related safety events, adverse device effects (ADEs) and serious adverse device effects (SADEs) can be found in Appendix 7.

AEs will be reported by the participant (or, when appropriate, by a caregiver, surrogate, or the participant's LAR).

The investigator or their designees are responsible for detecting, documenting and reporting events that meet the definition of an AE or SAE and remain responsible for following up.

The method of recording, evaluating, and assessing causality of AEs and SAEs and the procedures for completing and transmitting SAE reports are provided in Appendix 3.

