- Serum bilirubin fractionation should be performed if testing is available. If serum bilirubin fractionation is not immediately available, discontinue study intervention for that participant if ALT ≥3xULN and total bilirubin ≥ 2xULN. Additionally, if serum bilirubin fractionation testing is unavailable, record presence of detectable urinary bilirubin on dipstick, indicating direct bilirubin elevations and suggesting liver injury.
- All events of ALT ≥ 3xULN and bilirubin ≥ 2xULN (>35% direct bilirubin) or ALT ≥ 3xULN and INR>1.5 which may indicate severe liver injury (possible 'Hy's Law'), must be reported to GSK as an SAE; the INR threshold value stated will not apply to participants receiving anticoagulants
- 3. New or worsening symptoms believed to be related to liver injury (such as fatigue, nausea, vomiting, right upper quadrant pain or tenderness, or jaundice) or believed to be related to hypersensitivity (such as fever, rash or eosinophilia).
- 4. Includes: hepatitis A Immunoglobulin M (IgM) antibody; HbsAg and HbcAb; hepatitis C RNA; cytomegalovirus IgM antibody; Epstein-Barr viral capsid antigen IgM antibody (or if unavailable, heterophile antibody or monospot testing); and hepatitis E IgM antibody. In those with underlying chronic hepatitis B at study entry (identified by positive hepatitis B surface antigen) quantitative hepatitis B DNA and hepatitis delta antibody. If hepatitis delta antibody assay cannot be performed, it can be replaced with a polymerase chain reaction (PCR) of hepatitis D RNA virus (where needed) [Le Gal, 2005].
- 5. Record the date/time of the PK blood sample draw and the date/time of the last dose of study intervention prior to the PK blood sample draw on the CRF. If the date or time of the last dose is unclear, provide the participant's best approximation. If the date/time of the last dose cannot be approximated OR a PK sample cannot be collected in the time period indicated above, do not obtain a PK sample. Instructions for sample handling and shipping are in the central laboratory manual.

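### The possible-Hy's-Law SAE rule exempts participants on anticoagulants from the INR limb in two protocol sections but not in the other two (minor, needs reconciling)

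*Protocol*

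**What the plan says.** The protocol states the possible-Hy's-Law reporting duty in four places.

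- **10.3.2, item g (SAE definition):** "Possible Hy's Law case: ALT≥3x ULN AND total bilirubin ≥2x ULN (>35% direct bilirubin) or INR >1.5 must be reported as SAE". There is no exemption and no cross-reference. Section 8.4 sends sites here: "The definitions of an AE and SAE can be found in Appendix 3".
- **10.2, Appendix Table 1, footnote 2:** the duty covers every event of "ALT ≥3 × ULN and international normalized ratio(INR) >1.5, if INR measured, which may indicate severe liver injury (possible Hy's Law), must be reported". The only qualifier is that INR was measured.
- **7.1.2, notes to Figures 2 and 3:** "If possible Hy's Law case: ALT≥3xULN and total bilirubin ≥2xULN (>35% direct) or INR>1.5* report as an SAE". The asterisk leads to: "INR value not applicable to participants on anticoagulants".
- **10.6.1, footnote 2 (Appendix 6):** the same duty, ending with the proviso that "the INR threshold value stated will not apply to participants receiving anticoagulants".

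**The concern.** These are four statements of one mandatory rule, and they differ on whether the INR limb applies to someone taking an anticoagulant. In such a participant an INR above 1.5 may reflect the anticoagulant rather than the liver, which bears directly on what the INR limb is meant to detect.

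At stake is the consistency of a safety endpoint. Incidence of AEs and SAEs is a stated safety endpoint (protocol 3.1). SAEs are counted in the SAP's adverse event overview (4.5.2) and form a category of the benefit-risk forest plot (4.9). Two sites with identical participants could classify them differently, each following the protocol as written.

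**Working it through.** No figure in the plan needs reproducing. The check is a comparison of texts.

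**Step 1. The four statements side by side.**

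| Section | INR limb tied explicitly to ALT ≥3xULN? | Anticoagulant exemption? |
|---|---|---|
| 10.3.2, item g | Not repeated before INR | No |
| 10.2, footnote 2 | Yes | No |
| 7.1.2, figure notes | Not repeated before INR | Yes |
| 10.6.1, footnote 2 | Yes | Yes |

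**Step 2. Test case.** A participant on an anticoagulant has ALT ≥3xULN, total bilirubin <2xULN, INR >1.5 and no other seriousness criterion. Under 10.3.2 and 10.2 this must be reported as an SAE. Under 7.1.2 and 10.6.1 the INR threshold does not apply, so it is not an SAE on that ground.

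**Step 3. Does a cross-reference settle it?**

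- Section 8.4 leads to Appendix 3, which has no exemption.
- The action list in 10.6.1 tells sites to complete the SAE form if the event meets the SAE criteria. It marks that instruction with footnote 2, which has the exemption.
- The 10.2 footnote does point to the exempting sections, but for stopping criteria and what follows from them: "required actions and follow-up assessments after liver stopping or monitoring event are given in Section 7.1.2 and Appendix 6". Its SAE sentence is separate and covers all events.

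Each route therefore gives its own answer, and no text ranks them.

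**Step 4. Can the case occur?** Yes. Anticoagulants are not listed in the exclusion criteria (5.2) or in Table 4 (6.8.2). There is no upper age limit (5.1), and cardiac disease excludes only if uncontrolled (5.2, criterion 18). INR is not in the routine chemistry panel of Appendix Table 1. It is required in follow-up of a liver stopping event (10.6.1) and in the weekly repeats after a liver monitoring event (10.6.2), so it will be available when the rule is applied.

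**Step 5. How often?** The documents give neither the frequency of anticoagulant use nor that of ALT ≥3xULN. Assume, purely for scale, that 1–5% of the 250 participants take an anticoagulant and, independently, that 1–3% reach ALT ≥3xULN:

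- low: 250 × 0.01 × 0.01 = 0.025
- high: 250 × 0.05 × 0.03 = 0.375

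Within those inputs both figures are ceilings. They treat every such participant as having INR >1.5 and none as an SAE for another reason. Both are below one participant.

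**Step 6. What differs between the two readings?** Only the SAE label. The notes under both figures in 7.1.2 require reporting within 24 hours, so the liver event reaches the sponsor on that timescale whether or not the INR limb applies.

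**The case against.** The strongest reply is that a site handling a raised ALT is steered to the version with the exemption. The notes in 7.1.2 direct sites to the liver appendix, and that appendix attaches footnote 2 to the SAE step. Because INR is requested only in liver follow-up, a site holding a protocol INR is normally already working in Appendix 6. Local anticoagulation monitoring is the main other source. On this view the two shorter statements merely omit a footnote.

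Much of this stands. It makes conflicting classifications less likely and is a good reason to treat the point as minor. It does not remove the conflict, because 8.4 names Appendix 3 as the source of the SAE definition, and that definition is unconditional.

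A reader might also infer that a single INR-driven case would dominate the trial's liver safety assessment. The documents do not support this. The SAP's liver plot sets maximum ALT against maximum total bilirubin (4.5.3.1), which an anticoagulant-raised INR does not affect, and no INR-based Hy's Law count is planned. The investigator must also consider concomitant therapy as an alternative cause (10.3.4), and the rule concerns possible cases, not confirmed ones.

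**Conclusion.** The inconsistency is real: two mandatory statements of the rule classify the same participant in opposite ways, and the protocol does not say which governs. It is an error of internal consistency rather than a debatable design choice.

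Its weight is minor. It affects only anticoagulated participants who also reach ALT ≥3xULN and have no other reason to be an SAE. It does not touch any efficacy estimate, significance level or sample size.

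Two further readings should be resisted. One is that liver injury could go unreported. A case meeting the bilirubin limb is an SAE in all four sections, and an INR-only case is still reported as a liver event. The other is that any raised INR triggers the rule. Item g is loosely punctuated, but 10.2 and 10.6.1 both tie INR to ALT ≥3xULN, and that is the natural reading throughout.

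The conclusion about the conflict rests on the protocol text alone. Only the sense of rarity uses assumed frequencies.

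**What to change.** Reconcile the four passages so that one identically worded rule on the INR limb and anticoagulant use appears in 7.1.2 (notes to both figures), 10.2 footnote 2, 10.3.2 item g and 10.6.1 footnote 2. Which rule to adopt is for the sponsor's safety team. That team should note that footnote 2 in 10.6.1 is also marked against the INR row of the liver stopping criteria, so changing it there would reach beyond SAE reporting.

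In 10.3.2 item g, repeat ALT ≥3xULN before the INR limb, as 10.2 and 10.6.1 already do. Using the same wording in 7.1.2 removes the same looseness there.

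The cost is a few wording edits in the protocol. No assessment, data collection or SAP analysis changes.
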